## 7.4 End of Treatment (EOT) Visit

The following tests and procedures will be performed during the EOT visit. For all subjects the EOT visit should happen as soon as possible after the last dose of GTx-024 has been taken and no later than 3 days after that:

- Review of concomitant medications
- Physical examination, including weight and vital signs (heart rate, respiratory rate, temperature, blood pressure in a sitting position)
- ECOG performance status
- Blood sampling for: hematology, biochemistry, serum lipid profile, coagulation status, and serum hormones
- Blood sampling for specific blood tests: PSA and CTCs (enumeration and gene expression)
- Urine analysis, if clinically indicated
- Urine pregnancy test for premenopausal subjects (at the site)
- AE collection
- Radiological evaluation of the breast cancer (as applicable CT/MRI/bone scan). Imaging results will be confirmed by a central imaging facility. The same imaging technique must be used throughout the study in a given subject. The central imaging facility will also perform tumor volumetric assessment for the subjects undergoing CT scanning
- Subjects will be asked to complete a QoL questionnaire

Protocol: A Phase 2 Open Label, Multi-Center, Multinational Study Investigating The Efficacy and Safety Of GTx-024 On Advanced, Androgen Receptor-Positive Triple Negative Breast Cancer (AR+ TNBC)	Compound No.: GTx-024 Author: [name]
---	---

- GTx-024 drug accountability

## 7.5 Post-treatment Follow-up

Subjects will be followed up for 1 month after the last dose of GTx-024. They will undergo the following procedures:

- Review of concomitant medications
- Physical examination, including weight, vital signs (heart rate, respiratory rate, temperature, blood pressure in a sitting position)
- ECOG performance status
- Blood sampling for: hematology, biochemistry
- Blood sampling for PSA
- Urine analysis, if clinically indicated
- Urine pregnancy test for premenopausal subjects (at the site)
- AE collection

Subjects who continue to demonstrate a beneficial response from the study treatment at 12 months will be offered to continue in a safety extension study under a separate protocol.

### Long Term Follow-Up

All subjects will be followed for vital status. For those subjects that discontinue prior to twelve (12) months of study treatment, vital status will be obtained by chart review or by telephone every 60 days from the date study treatment was discontinued. For subjects that die during the Long Term Follow Up period, the date of death will be collected. Vital status will be followed on all patients for up to 24 months post the discontinuation of study treatment.

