Week/Day				Day 28 (± 7 days)	Day 56 (± 7 days)	Day 84 (± 7 days)	Day 112 (± 7 days)	Day 140 (± 7 days)	Day 168 (± 7 days)	Day 196 (± 7 days)	Every 8 weeks (± 7 days)	3 days after the last dose of GTx-024	
Procedure													
AEs	X	X		X	X	X	X		X		X	X	To be followed up to 28 days post treatment
Serum pregnancy test	X												
Urine pregnancy test 		X		X	X	X	X		X		X	X	X
GTx-024 18 mg dispensing/ administration		X 			X		X		X		X		
GTx-024 18 mg accountability				X	X	X	X		X		X	X	
QoL EQ-5D-5L		X		X	X	X	X		X		X	X	

Protocol: A Phase 2 Open Label, Multi-Center, Multinational Study Investigating The Efficacy and Safety Of GTx-024 On Advanced, Androgen Receptor-Positive Triple Negative Breast Cancer (AR+ TNBC)

Compound No.: GTx-024  
Author: [name]

Periods	Screening Day -28 to -1	Baseline Day 1	Safety check	Treatment phase  (from Baseline to EOT)								EOT/ Early termination	FU post treatment
				V3	V4	V5	V6	V7	V8	V9	As required if still on treatment		
Visit number	V1	V2	Safety review Week 2 (± 3 days)	Week 4	Week 8	Week 12	Week 16	Week 20	Week 24	Week 28	V10-V12 	VEOT	VFU
Week/Day				Week 4	Week 8	Week 12	Week 16	Week 20	Week 24	Week 28	Every 8 weeks (± 7 days)	3 days after the last dose of GTx-024	
Procedure				Day 28 (± 7 days)	Day 56 (± 7 days)	Day 84 (± 7 days)	Day 112 (± 7 days)	Day 140 (± 7 days)	Day 168 (± 7 days)	Day 196 (± 7 days)			
28 (± 2 days) Follow-up after last dose													X
Vital Status Follow up (every 60 days after last dose) 													X

 Subjects with clinical benefit at 16 weeks will continue on therapy for up to 12 months (as long as they still benefit from the treatment during these 12 months). If so, the subjects will be asked to come for a visit every other month and undergo the assessments for the treatment period.

 Visit 10 should occur at Week 32; i.e., 8 weeks after Visit 8 (Week 24).

 AR status to be checked via nuclear AR staining by IHC, only if not available in the medical record of the subject. This assessment will be done in a local/regional laboratory. AR status assessed locally (or as per medical record) will be used to determine subject eligibility during. Prescreening or the study screening period. AR status will be confirmed by a central laboratory prior to Visit 2 (Day 1).

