 These medical procedures and assessments do not have to be repeated if done at screening within 7 days before the first dose of study treatment.

 Vital Status Follow up (every 60 days after last dose) for up to 24 months

Protocol: A Phase 2 Open Label, Multi-Center, Multinational Study Investigating The Efficacy and Safety Of GTx-024 On Advanced, Androgen Receptor-Positive Triple Negative Breast Cancer (AR+ TNBC)
	
Compound No.: GTx-024 Author: [name]

--	---

 HBV screening will be done as HBsAg.

 Imaging study (CT, MRI) is recommended to be performed within 7 days prior to the first dose of study treatment. The imaging studies will be assessed by both a local imaging facility and a central reader. Subject eligibility will be based on local reading of the imaging studies. Medical decisions will be based on the local assessments.

At visits V1, V6, V8, and EOT, tumor volumetric assessments will be done for the subjects undergoing CT scanning.

 In compliance with RECIST 1.1 guidelines, subjects who have CR or PR at week 16 and/or week 24 require confirmation within a month as follows:

- For subjects with measurable lesions, subjects will undergo CT/MRI based on the Investigator's medical judgment

 Bone scans will be performed at screening and then at weeks 8, 16, and 24 in only those subjects with baseline bone metastases, or if clinically indicated.

 In compliance with RECIST 1.1 guidelines, subjects who have CR or PR at week 16 and/or week 24 require confirmation within a month as follows:

- For subjects with non-measurable lesions, subjects will undergo X-ray or bone-scanning based on the Investigator's medical judgment and location of disease.

 Blood sampling for pharmacokinetic assessment. The exact time (hh:mm) and date of the blood sample should be recorded on the eCRF. At the baseline visit, the blood sample should be collected before the subject is given their first dose of GTx-024. At visits 3 (week 4), 5 (week 12), 6 (week 16), and 8 (week 24), the date and approximate time of the last dose of GTx-024 prior to the blood sample should also be recorded; i.e., it should be documented whether the subject took the previous dose that morning or the evening before.

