observed in subjects with elevated ALT levels. Consistent with the effects of other orally administered anabolic agents, GTx-024 causes a dose dependent reduction in high-density lipoprotein (HDL), the clinical significance of which is unknown at this time. The proposed mechanism for reduction in HDL is due to stimulation of reverse cholesterol transport and increased HDL catabolism by hepatic lipase. Reductions in HDL are temporary and typically return to baseline 12 months after treatment initiation.

There were no other consistent, clinically relevant, dose-related effects of GTx-024 on ECGs or vital signs measurements (blood pressure or heart rate).

Investigators should be aware that blood levels of the tumor marker, CA27.29, have been shown to be modulated by compounds with androgenic activity as a result of the marker binding to the androgen regulated protein MUC-1. As a result, administration of GTx-024 has the potential to result in increases in CA27.29 that are not necessarily reflective of disease progression.

The drug used in this research study may affect a fetus. Subjects should not become pregnant nor breastfeed a baby while participating in this research study. Counselling about preventing pregnancy will be provided, if necessary, to study participants.

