10. Negative serum pregnancy test in women of childbearing potential (premenopausal or less than 12 months of amenorrhea post-menopause, and who have not undergone surgical sterilization), no more than 7 days before the first dose of study treatment;
11. For women of childbearing potential who are sexually active, agreement to use a highly effective, non-hormonal form of contraception during and for at least 6 months after completion of study treatment; OR, a fertile male partner willing and able to use effective non-hormonal means of contraception (barrier method of contraception in conjunction with spermicidal jelly, or surgical sterilization) during and for at least 6 months after completion of study treatment;
12. Adequate organ function as shown by:
  - Absolute neutrophil count  $\geq 1,000$  cells/mm^3
  - Platelet count  $\geq 100,000$  cells/mm^3
  - Hemoglobin  $\geq 9$  g/dL
  - Serum aspartate aminotransferase (AST) and ALT  $\leq 2.5$  ULN (or  $\leq 5$  if hepatic metastases are present)
  - Total serum bilirubin  $\leq 2.0 \times$  ULN (unless the subject has documented Gilbert Syndrome)
  - Alkaline phosphatase levels  $\leq 2.5 \times$  ULN ( $\leq 5 \times$  ULN in subjects with liver metastasis)
  - Serum creatinine  $\leq 2.0$  mg/dL or 177  $\mu$ mol/L
  - International normalized ratio (INR) or activated partial thromboplastin time (aPTT)  $< 1.5 \times$  ULN (unless on anticoagulant treatment at screening);
13. Able to swallow capsules;
14. Any toxicity from prior chemotherapy has resolved or is Grade 1 (NCI-CTCAE, Version 4.0).

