#### 9.2.4 Reporting of Pregnancy

If a subject becomes pregnant during the study, she must be instructed to stop taking the study drug and immediately inform the Investigator. The Investigator must report all pregnancies within **24 hours** to the Sponsor as per [Section 9.2 Reporting Procedures](#) regardless of seriousness. The Investigator should counsel the subject and discuss the risks of continuing with the pregnancy and the possible effects on the fetus. Monitoring of the subject should continue until conclusion of the pregnancy. The clinical outcome of the pregnancy should be documented. Specifically, the estimated date of conception, expected date of delivery, actual date of delivery, date of last menstrual period, and details of contraceptives should be documented. The pregnancy course should be described in full. If the subject gives birth, the weight and length of the child, Apgar scores (with explanation of score  $< 10$ ), and congenital abnormalities should be documented. Concomitant drugs and medical history of the mother should be documented. Smoking status and alcohol intake during pregnancy and illicit drug use prior to and during pregnancy should be recorded. Pregnancy will be followed until completion. If the new-born is healthy, additional follow-up is not necessary.

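### After the 28-day visit no scheduled step looks for pregnancy, although contraception is required for at least 6 months after treatment

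*Combined protocol and SAP*

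**What the plan says.** **Contraception.** Criterion 11 in Section 5.1 applies to sexually active women of childbearing potential and runs "during and for at least 6 months after completion of study treatment". Criterion 10 defines that group as "premenopausal or less than 12 months of amenorrhea post-menopause, and who have not undergone surgical sterilization". Section 2.3.1 gives the reason for caution: "The drug used in this research study may affect a fetus". No reason is given for choosing 6 months.

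**Testing.** Urine pregnancy tests are scheduled for premenopausal subjects at treatment visits, at end of treatment, and at the post-treatment visit, which the Schedule of Events lists as "28 (± 2 days) Follow-up after last dose". Collection of adverse events and serious adverse events stops at the same point, 28 days after the last dose (Sections 9.2.1 and 9.3).

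**Later follow-up.** For subjects who stop before 12 months, Section 7.5 (Long Term Follow-Up) says "vital status will be obtained by chart review or by telephone every 60 days from the date study treatment was discontinued". It adds only that the date of death is recorded. Section 4 and footnote 5 of the Schedule of Events extend the interval to all subjects: "Vital Status Follow up (every 60 days after last dose) for up to 24 months".

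**Reporting.** Section 9.2.4 places a duty on the subject: "If a subject becomes pregnant during the study, she must be instructed to stop taking the study drug and immediately inform the Investigator". It places a separate one on the site: "The Investigator must report all pregnancies within" 24 hours, regardless of seriousness. The pregnancy is then followed to completion, and any congenital abnormality is documented.

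**The concern.** The protocol treats the 6 months after the last dose as a period in which conception should be prevented. It also wants the outcome of any pregnancy recorded in detail. Yet from roughly month 2 to month 6 nothing in the visible schedule would bring a pregnancy to the site's notice. The site would learn of one only if the woman volunteered it, or if it happened to appear in a chart opened to check whether she was alive.

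Her own instruction to inform the site applies during the study, a term the protocol does not define. The Protocol Summary describes participation as screening, treatment and a 1-month follow-up, so the duty could be read as ending at about day 28.

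What is at stake is safety information on fetal exposure, not efficacy. Such an event would be rare, but a missed one could not easily be recovered later.

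**Working it through.** The plan gives no figure on this point to reproduce. The check is a day count, followed by a rough expected number.

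**1. Length of the gap.** Contraception period: at least 6 months, taken as 182 days. Last test: day 28, with a window of ±2 days.
- 182 − 28 = 154 days.
- With the visit window: 182 − 30 = 152 to 182 − 26 = 156 days.

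This is calendar time between the last test and the end of the required period. It is not a count of missed conceptions, and a test at day 28 does not exclude a conception a few days earlier.

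**2. What falls inside the gap.** Counting 60-day intervals from the last dose, vital-status checks fall at days 60, 120 and 180, with the next at day 240. As written, each may be a chart review, and none includes a pregnancy item. The Schedule of Events puts the urine test and the vital-status row in the same follow-up column, but Section 7.5 ties the test to the 1-month visit, so the table does not schedule tests at the later checks.

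**3. How long to keep asking.** Assume a pregnancy is recognised 28 to 42 days after conception (an assumption, not from the documents).
- If the last question is at day 180, conceptions after day 180 − 28 = 152, or after day 180 − 42 = 138, are missed. That is 182 − 152 = 30 to 182 − 138 = 44 days, or 30/154 = 19% to 44/154 = 29% of the gap.
- If the last question is at day 240, a conception on day 182 is 240 − 182 = 58 days old. That exceeds 42, so none is missed under this assumption.
- The Protocol Summary could be read as starting the 60-day count after the 1-month visit, giving days 88, 148, 208 and 268. Day 208 is then only 208 − 182 = 26 days past the window, so the day-268 check would be needed. Either way there are four questions per woman.

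**4. Expected number of pregnancies in the gap.** Formula: subjects × share of childbearing potential × pregnancies per woman-year × years × share of the window lived through. Enrollment of 21 to 55 comes from Section 4. The other inputs are assumptions: 25% to 50% of childbearing potential, 0.5% to 5% per woman-year, and 50% to 100% of the window lived through. Time is 154/365.25 = 0.42 years.
- Low: 21 × 0.25 × 0.005 × 0.42 × 0.5 = 0.006.
- High: 55 × 0.50 × 0.05 × 0.42 × 1 = 0.58.

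The high figure is a ceiling for these inputs: full enrollment, no deaths, and every such woman sexually active.

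**5. Number of questions.** 21 × 0.25 is about 5 women and 55 × 0.50 is about 28. At four questions each: 5 × 4 = 20 to 28 × 4 = 112. If all 55 subjects were of childbearing potential, the limit is 55 × 4 = 220.

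**The case against.** The strongest reply is that the protocol already has prevention (criterion 11, and counselling under Section 2.3.1), a self-report instruction, and an Investigator duty with no 28-day limit. Nothing in the documents says that active questioning must last as long as contraception. The consent pages, which were not available, are a natural place to tell women to report a later pregnancy. No elimination or reproductive-toxicity data are given, so a drug-related risk in months 2 to 6 is not shown. Many subjects may move to other anticancer treatment, which would blur attribution. The expected count is very small and rests on assumed inputs.

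Most of this stands, and it sets the priority. It does not supply a step that would find a pregnancy: each existing safeguard depends on the site happening to hear of it.

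Three stronger readings are tempting and should be resisted:
- *Pregnancies after day 28 need not be reported.* Section 9.2.4 covers all pregnancies and sets no such cutoff.
- *The site already speaks to every woman every 60 days, so a question costs nothing.* Chart review satisfies the protocol, so contact is not guaranteed, and the remedy changes how some checks are done.
- *Most of the risk goes undetected because 154 of 182 days are uncovered.* The day count measures the calendar, not risk.

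**Conclusion.** The point holds as a gap in detection. After day 28 (±2), about 154 calendar days (152 to 156) of the required contraception period have no scheduled pregnancy test or question in the visible protocol. A secondary weakness is that the subject's duty to inform the site has no defined end.

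The practical size is small: 0.006 to 0.6 expected pregnancies under the assumptions above, so fewer than one. The primary analysis and the two-stage rule are unaffected.

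The conclusion is limited to the visible text. The consent form may already cover self-report, although that would still be passive. Subjects who enter the extension study fall under a separate protocol that was not available. Minor priority, moderate confidence; the case for change rests on low cost and on the seriousness of a missed fetal outcome, not on frequency.

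**What to change.** 1. **Section 7.5, Long Term Follow-Up.** For women meeting the criterion 10 definition, make the 60-day vital-status checks telephone contacts where possible, through the first one after month 6 (about day 240, or day 268 if the count starts at the 1-month visit). Add one pregnancy question to each, with a chart check as fallback. Using criterion 10 also covers women with less than 12 months of amenorrhea, whom the premenopausal wording for the urine tests may not clearly include.
2. **Section 9.2.4.** Keep the stop-drug instruction for women on treatment. Add that any pregnancy conceived from the first dose until 6 months after the last dose is to be notified by the subject, reported within 24 hours of the Investigator learning of it, and followed to outcome. Check that the consent form says the same.

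**Cost.** Amendment wording, one eCRF field, and some short calls in place of chart review: about 20 to 112 questions under the assumed numbers of women, at most 220, and fewer with deaths. No added visit or laboratory test.

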## 7.6 Early Termination Visit

An early termination visit will happen in case of:

- A subject withdrawing from the study at their decision
- GTx, Inc. terminating the study in the interest of subject welfare
- Investigator withdrawing the subject from the study

Subjects will be asked to attend a final visit so that the procedures for the EOT (see above) may be performed.

Protocol: A Phase 2 Open Label, Multi-Center, Multinational Study Investigating The Efficacy and Safety Of GTx-024 On Advanced, Androgen Receptor-Positive Triple Negative Breast Cancer (AR+ TNBC)	Compound No.: GTx-024 Author: [name]
---	---

## 7.7 Safety Checks and Unscheduled Visits

A page will be included in the eCRF that asks whether any unscheduled visits have taken place and provides space for the recording of any collected data, including unscheduled vital signs, ECG, and laboratory results. Early/late planned visits will not be considered to be unscheduled visits.

The laboratory results from the safety checks in Weeks 2 and 3 will be recorded on the unscheduled visit eCRF page.

Protocol: A Phase 2 Open Label, Multi-Center, Multinational Study Investigating The Efficacy and Safety Of GTx-024 On Advanced, Androgen Receptor-Positive Triple Negative Breast Cancer (AR+ TNBC)	Compound No.: GTx-024 Author: [name]
---	---

## 8 STUDY PROCEDURES/EVALUATIONS

Please see APPENDIX A: SCHEDULE OF EVENTS for an outline of the timing of the study procedures/evaluations.

### 8.1 Clinical Evaluations

All treatment decisions will be based on Investigator assessments, including determination of PD.

#### Imaging Assessments:

CT (and/or MRI) imaging scans of the brain, chest, abdomen, and pelvis should be contiguous throughout all the anatomic region of interest. For the purposes of this trial, CT scans with intravenous contrast enhancement are the preferred anatomic imaging modality. MRI scans with contrast of the brain, abdomen and pelvis may be used in lieu of CT scans for patients who are unable to receive an intravenous iodine contrast agent; however, MRI exams of the chest are not recommended. In these cases, a non-contrast CT of the chest is recommended to evaluate the lung parenchyma. Whichever imaging method is selected should be used for all study assessments in a given subject.

Bone scintigraphy (bone scans) will be performed to assess bone metastases. Bone scans will be performed at screening and then at weeks 8, 16, and 24 in only those subjects with baseline bone metastases, or if clinically indicated.

Tumor lesions will be assessed using RECIST 1.1 at the site based on the local reading facility. Scans will be sent to the central imaging facility for final efficacy outcomes analysis.

Tumor volumetrics will be performed by the assigned central vendor only for subjects who have CT scans at Visits 1, 6, 8, and EOT. Tumor volumetrics will be performed by an independent 3rd party vendor who is masked to individual subject outcomes.

#### Medical History and Medication History:

The medical history of the subject will be obtained by the PI from the subject's medical record. Medication history will include all medications currently being taken (rather than the lifelong medication history) and will include both prescription and over-the-counter medicines (also including nutritional supplements or herbal treatments). This will include prior cancer treatments taken.

Protocol: A Phase 2 Open Label, Multi-Center, Multinational Study Investigating The Efficacy and Safety Of GTx-024 On Advanced, Androgen Receptor-Positive Triple Negative Breast Cancer (AR+ TNBC)	Compound No.: GTx-024 Author: [name]
---	---

**Physical Examination:**

Physical examination will include measurement of height, weight, body temperature, respiratory rate, blood pressure, and heart rate.

Vital signs may be taken at any other times. Blood pressure and heart rate measurements will be performed with subjects in a seated position. AEs will be followed-up to resolution, and while further physical examinations may take place, they will not be mandatory.

The physical examination will include also ECOG performance status.

